4. STUDY POPULATION

4.1 Population (base)

Couples diagnosed with unexplained or mild male infertility in whom the woman is >=20 years old.

4.2 Inclusion criteria

In order to be eligible to participate in this study, a participating couple must meet all of the following criteria:

- Being diagnosed with unexplained or mild male infertility
- At least one sided tubal patency, established according to local protocol
- Normal or mild impairment of semen quality defined as sperm concentration above 5 million per millilitre or progressive motility sperm no less than 10%, based on at

4.3 Exclusion criteria

A potential participant who meets any of the following criteria will be excluded from study participation:

- Woman with double sided tubal pathology
- Women with irregular cycles, PCOS or other endocrine disorders
- Man with impaired semen quality: sperm concentration lower than 5 million per millilitre or progressive motility sperm less than 10%
- Women younger than 20 years old

4.4 Sample size calculation

Our sample size is based on an cumulative live birth rate. We anticipate an 18% pregnancy rate after 3 cycles natural cycle IUI. We presume that the clinical relevant difference is 8%. To test the hypothesis that IUI with letrozole increased the pregnancy rate to 26% as compared to natural cycle IUI, we need to include 483 women per arm (total 966). (two sided-test, alpha .05, beta .80, 15% loss to follow-up). Firstly we will collect 100 women for a pilot study.

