Intervention Women will be randomized for ovarian stimulation with letrozole or to natural cycle IUI. In the group allocated to ovarian stimulation, women will receive oral tablets letrozole 5 mg daily from cycle day 3-5 for 5 days. We will treat the couples for 3 cycles, with a time horizon of 4 months.

Main study parameters/endpoints

Primary outcome is ongoing pregnancy leading to live birth. Secondary endpoints are clinical pregnancy, multiple pregnancy, miscarriage rates, pregnancy complications and patients' costs.

Nature and extent of the burden and risks associated with participation, benefit and group relatedness

The strategies compared are already broadly applied in current practice. No additional risks are expected. There is no benefit for participants, but the results may benefit future subfertile couples

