6.1.2 Secondary study parameters/endpoints (if applicable)

- 1. Number of cycles with mono-follicular growth
- 2. Number of cycles with Multiple follicular growth
- 3. Number of cancelled cycles due to the occurrence of >3 follicles >15 mm
- 4. Time to conception leading to live birth
- 5. Clinical pregnancy
- 6. Miscarriage
- 7. Multiple pregnancy (reported as twins and higher order multipl
- 8. PregNANCY COMPLICATIONS
- 9. Direct and indirect costs

Counselling

Women eligible for participation in the study will be invited for additional counselling by a research nurse, to ensure that they are fully informed on the nature of the study by means of written information (Participant Information Form). Women who agree to participate will be asked to sign a written informed consent of which they will receive a copy. Consenting eligible women will be randomly allocated to one of the two strategies at the baseline visit of the first treatment cycle.

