8. STATISTICAL ANALYSIS

Step 1: Summarizing trial data.

Baseline data and outcome data will be separately summarized. For continuous variables, we will examine the distribution of the observations, and if normally distributed then we will summarize them as means with standard deviations (SDs). If they are not normally distributed, then medians and inter-quartile ranges (IRQs) will be reported. For dichotomous data, we will provide proportions (or percentages). In addition to the baseline and outcome data, we will also summarize the recruitment numbers, those lost to follow-up, protocol violations and other relevant data.

Step 2: Inter-group comparisons.

The analysis of all outcomes will be done on an intention to treat basis.

The effectiveness of IUI with letrozole versus IUI in natural cycle will be expressed as a rate ratio for live birth with corresponding 95% confidence intervals. A formal test of the difference in rate will be performed using chi-square test statistics. The effectiveness over time will be evaluated in life tables and differences in live birth over time will be evaluated using the log-rank test. Further dichotomous outcomes will be analyzed using either Fishers Exact Test or chi-square as appropriate. For continuous outcomes we will use t-test if the observations in each trial arm are normally distributed, and if non-normally distributed, then Mann-Whitney-U test will be employed. Although p-values will be reported, the focus will be on providing 95% confidence intervals around point estimates as these are more useful in interpreting the findings of the trial.

Step 3: Adjustments and sensitivity analyses.

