If randomization fails to achieve balanced groups, then we will perform secondary analyses in which we will adjust for unbalanced prognostic factors using procedures such as logistic regression. If the primary unadjusted analysis and secondary adjusted analysis are discordant, we will give greater weighting to the primary analysis in the interpretation of trial findings. For issues such losses to follow-up, missing data, and protocol violations, we will attempt sensitivity ("worst-case scenario") analyses to explore the effect of these factors on the trial findings. As a secondary analysis, we will adjust for missing data using imputation techniques to explore the effects of such imputations on the trial findings. The effect of baseline characteristics on the primary outcome will be explored using logistic regression analysis. In sub analyses the association between follicular growth and live birth will be evaluated.

Details of the analysis will be described in a separate statistical analysis plan, that will be developed during the study, and finalized before data lock.

Interim Analysis

Interim analysis will be done after completion data recruitment of the first 50 participants. An independent Data Safety Monitoring Committee (DSMC) will be invited. The DSMC will be asked to assess the endpoint ongoing pregnancy, as data on live birth will not be available. Also, the DSMC will be provided insight in the SAE's that have occurred. The continuation of the study will depend on the advice of DSMC. A formal stopping rule will be formulated in the separate statistical analysis plan.

Economic evaluation

An economic analysis will be performed alongside the clinical trial. The economic analysis will be performed from a healthcare perspective. Depending on the outcome of live birth rates in both groups, the economic analysis will be a cost-minimization of cost-effectiveness analysis.

Cost-effectiveness of each strategy will be presented as cost per live birth and costs

pre clinical pregnancy. Robustness of the results for various assumptions and parameter estimates will be explored in sensitivity analysis outcomes and will be expressed in ICER graphs and cost-effectiveness acceptability curves. A decision model will be used to evaluate the optimal strategy.

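### Section 4.4: 483 per arm gives about 79% power, not 80%, after 15% loss (lost women excluded); beta is misprinted as .80, and live birth inputs are labelled pregnancy rates

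*Combined protocol and SAP*

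**What the plan says.** Section 4.4 (Sample size calculation) opens with "Our sample size is based on an cumulative live birth rate". It continues "We anticipate an 18% pregnancy rate after 3 cycles natural cycle IUI", takes 8 percentage points as the relevant difference, so that the letrozole rate is 26%, and ends with "we need to include 483 women per arm (total 966). (two sided-test, alpha .05, beta .80, 15% loss to follow-up". It gives no formula, no number before the loss allowance and no method for applying that allowance.

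The Summary, under main study parameters, states "Primary outcome is ongoing pregnancy leading to live birth", and section 6.1.1 agrees. Section 6.1.2 lists "5. Clinical pregnancy" as a secondary endpoint and miscarriage as another, so the protocol treats pregnancy and live birth as different outcomes.

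Section 8, Step 2, names a chi-square test for live birth and states "The analysis of all outcomes will be done on an intention to treat basis". Neither Step 2 nor Step 3 says how a woman lost to follow-up is counted in the primary analysis. Step 3 offers worst-case analyses as sensitivity work and imputation as a secondary analysis. Section 8 then adds "Details of the analysis will be described in a separate statistical analysis plan", to be finalised before data lock.

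**The concern.** An allowance for loss should leave the required number of evaluable women after the loss has occurred. If 420 are needed and 15% are lost, the number to randomise is 420/0.85. Multiplying by 1.15 falls short, because 15% of the larger number is then lost.

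Two labels in the same paragraph also look wrong. Beta is the type II error, so a beta of .80 describes a trial that misses a true effect four times in five. And a calculation said to rest on live birth should not take rates labelled as pregnancy.

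This paragraph is the only stated basis for the power of the 966-woman trial. At stake is whether its own inputs give the power it claims, and whether that power refers to the primary endpoint.

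**Working it through.** **Inputs.** All are from section 4.4: p₁ = 0.18, p₂ = 0.26, difference 0.08, two-sided alpha 0.05 (z = 1.960), 15% loss, 483 per arm (1:1, total 966). Power is read as 0.80 (z = 0.842). The mean rate is p̄ = 0.22. The test is the chi-square of section 8, Step 2.

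**Reproducing the plan's figure.** The pooled two-proportion formula without continuity correction is

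n = [1.960·√(2p̄(1−p̄)) + 0.842·√(p₁(1−p₁) + p₂(1−p₂))]² / (p₂−p₁)²

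= [1.960 × 0.5858 + 0.842 × 0.5831]² / 0.0064 = (1.1482 + 0.4907)² / 0.0064 = 419.7, so 420 per arm.

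Then 420 × 1.15 = 483.0, the stated figure exactly.

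**Other routes to 483.** Each formula is at 80% power, rounded up:

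| Formula | n | n × 1.15 | n / 0.85 |
|---|---|---|---|
| Pooled, two-sided | 420 | 483 | 495 (494 from 419.7) |
| Unpooled | 417 | 480 | 491 |
| Common p̄ | 421 | 485 | 496 |
| Arcsine | 418 | 481 | 492 |
| Continuity-corrected | 445 | 512 | 524 (523 unrounded) |
| Pooled, one-sided | 331 | 381 | 390 |

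Only the pooled two-sided number multiplied by 1.15 gives 483. No version divided by 0.85 does.

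**Power at 483 per arm** (same formula solved for power):

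- 15% lost and excluded: 483 × 0.85 = 410.6 evaluable per arm, power 79.1%. Exact enumeration of the uncorrected chi-square test at 410 or 411 per arm gives 79.3%.
- 15% lost and counted as no live birth: the rates become 0.18 × 0.85 = 15.3% and 0.26 × 0.85 = 22.1% with 483 per arm, power 77.4%.
- Complete outcomes: power 85.2%.

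**Loss that 483 can absorb at 80% power.** With lost women excluded, 1 − 419.7/483 = 13.1%. With lost women counted as no live birth, about 10.5%.

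**Size needed for 80% at 15% loss.** With exclusion, 419.7/0.85 = 493.8 or 420/0.85 = 494.1, so 494–495 per arm (988–990 in total). With lost women counted as no live birth, the formula at 15.3% against 22.1% gives 514.9, so 515 per arm (1,030 in total). Under that second rule 494–495 gives only 78.3–78.4%.

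**Beta taken literally.** A beta of .80 is power .20, for which z = −0.842: n = (1.1482 − 0.4907)² / 0.0064 = 67.5, so 68 per arm, or 79–80 after either inflation. The stated 483 cannot come from it.

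**Endpoint label.** The first sentence of section 4.4 says live birth; the sentences giving 18% and 26% say pregnancy. No arithmetic can settle which is meant, and the documents give no source for either rate.

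**The case against.** The arithmetic is not in dispute; the objections concern weight and certainty.

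- **The slip is inferred and tiny.** No inflation method is stated. The gap between 483 and 495 is 12 women per arm (12/483 = 2.5%) and about 0.9 points of power, or 0.7 by the exact test. The inputs are round planning assumptions: a true difference of 8.1 points, or a control rate of 17% with the same 8-point difference, would bring power back to 80%. This stands, and it is why the point is minor. It does not make the stated power right: 483 with 15% lost is below 80% under both counting rules, however 483 was reached.
- **The 79% is conditional.** It needs lost women to be excluded, which the protocol does not state, and the 77% rests on an assumed rule that lost means no live birth. This stands too, so each figure should carry its condition. The intention-to-treat statement does not remove the shortfall: it leaves the counting rule open, and counting lost women as no live birth enlarges the gap.
- **The misprinted beta misleads nobody.** Probably so, but it is false as written and takes a moment to correct.
- **The endpoint label could matter more than the rest.** If 18% and 26% really are pregnancy rates, live birth rates would be lower. Assuming, purely for illustration, that 80–90% of pregnancies reach live birth (the documents give no figure), power at 483 after 15% exclusion would be about 67–74%. That is a fair reason to settle the label before restating any power. But the opening sentence and the primary endpoint both point to live birth, so a loss of power is possible rather than shown.
- **Section 3 plans for 100 women**, which section 4.4 calls a pilot. How that relates to the 966 is a separate question and does not answer this one.

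**Conclusion.** The concern holds and is minor. On its own inputs, section 4.4 does not deliver 80% power after 15% loss: it delivers 79.1% with lost women excluded or 77.4% with them counted as no live birth, against 85.2% with no loss. These figures assume equal loss in both arms, unrelated to outcome, and that 18% and 26% are live birth rates among women whose outcome would be known. That the allowance was multiplied rather than divided is an inference from an exact match; the shortfall does not depend on it.

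The printed beta is an error, since 483 reproduces only with power .80. The pregnancy label is an inconsistency with no demonstrated loss of power, but the sponsor must resolve it, because every figure above depends on the answer. None of this makes the trial materially underpowered if the rates are live birth rates.

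**What to change.** Rewrite the one paragraph in section 4.4:

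1. State first whether 18% and 26% are cumulative live birth rates. If they are not, re-derive the power for the primary endpoint.
2. Replace the beta entry with power .80 (beta .20).
3. Keep 966 and restate the power: about 79% after 15% loss if lost women are excluded, about 77% if they count as no live birth, about 85% with complete outcomes.
4. If a size is quoted instead, attach its condition: 494–495 per arm only when lost women are excluded, about 515 when they count as no live birth.
5. State how lost women are counted in the primary analysis, here or in the separate statistical analysis plan before data lock.

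Restating the power costs one corrected paragraph and no extra enrolment. The only downside is a slightly less favourable stated power. Restoring 80% through numbers would cost 22–24 more women in total with exclusion (988–990 against 966), or 64 more with lost women counted as no live birth (1,030 against 966).

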5. TREATMENT OF SUBJECTS

5.1 Investigational product/treatment

All women sighed informed consent are seen for a baseline visit with a transvaginal ultrasound at the third day of the menstrual cycle, at the first treatment cycle. At this first monitoring the antral follicle count will be measured and registered. Women are not allowed to continue if one (or more) ovarian cysts of >15 mm is seen. These women are treated further according to local protocol.

Eligible women will be randomly allocated to either 3 cycles of IUI with letrozole or IUI in natural cycle.

Medication will be perscribed by the treating physician.

Intervention

After randomisation, women will receive instructions to start daily oral tablets with 5mg letrozole for 5 days or without stimulation. Medicine therapy is started on day 3, 4 or 5 of the menstrual cycle depending on the length of the menstrual cycle and stopped after 5 days of daily intake of two tablets of 2.5 mg.

Subsequently further transvaginal ultrasounds will be scheduled to monitor follicle growth in both groups. As soon as at least one dominant follicle with a mean diameter of >18 mm is present, with a maximum of in total three follicles >15 mm ovulation will be triggered using 10000 IU hCG. At the final ultrasound the total number of follicles and their diameters will be measured and registered.

Ovulation triggering will be withheld if more than three follicles with a diameter of >15 mm are seen. In this case, the couples are also strictly advised to have barrier protected intercourse. Intrauterine insemination is scheduled 36-42 hours after ovulation triggering.

On the day of insemination the male partner will provide a semen sample by means of masturbation after a minimum of two days of sexual abstinence. The semen will be subjected to density gradient centrifugation and/or washing according to local laboratory protocol. Women who will not conceive will be scheduled for the second and subsequent insemination cycles, and will keep the same stimulation regimen up to 3 cycles after randomisation.

6. METHODS

6.1 Study parameters/endpoints

6.1.1 Main study parameter/endpoint

Ongoing pregnancy resulting in live birth, conceived within 3 cycles IUI after randomisation in a time horizon of 4 months. In calculation, we will take the

calculated moment of conception leading to the live birth

6.1.2 Secondary study parameters/endpoints (if applicable)

- 1. Number of cycles with mono-follicular growth
- 2. Number of cycles with Multiple follicular growth
- 3. Number of cancelled cycles due to the occurrence of >3 follicles >15 mm
- 4. Time to conception leading to live birth
- 5. Clinical pregnancy
- 6. Miscarriage
- 7. Multiple pregnancy (reported as twins and higher order multipl
- 8. PregNANCY COMPLICATIONS
- 9. Direct and indirect costs

Counselling

Women eligible for participation in the study will be invited for additional counselling by a research nurse, to ensure that they are fully informed on the nature of the study by means of written information (Participant Information Form). Women who agree to participate will be asked to sign a written informed consent of which they will receive a copy. Consenting eligible women will be randomly allocated to one of the two strategies at the baseline visit of the first treatment cycle.

6.2 Randomisation, blinding and treatment allocation

Randomization will be performed centrally with the use of envelope method.

The study will be completed 4 months after randomisation, with a maximum of 3 cycle attempts. According to local protocol, participants may be offered more IUI cycles, with medication to their preference after the 4 months study period, or proceed to IVF immediately.

The study will be open.

6.3 Study procedures

Data collection

The study will be performed by Reproductive Centre of Peking University Third Hospital that is familiar with randomised clinical trials. This has resulted in an infrastructure with research nurses, a secretary office for the handling of ethical approval, the use of web-based data-entry and collaborate analysis. All data will be registered in a case record form (CRF).

Baseline characteristics

From participant history

Duration of infertility, parity, referral status, weight, length, smoking. semen-analysis, tubal status

Ultrasound

We will record the basal antral follicle count using sonography and record the number and measurements of the total follicles seen at the final ultrasound just before or at the day of ovulation triggering.

6.4 Withdrawal of individual subjects

Subjects can leave the study at any time for any reason if they wish to do so without any consequences. The investigator can decide to withdraw a subject from the study for urgent medical reasons.

7. SAFETY REPORTING

7.1 Section 10 WMO event

In accordance to section 10, subsection 1, of the WMO, the investigator will inform the subjects and the reviewing accredited METC if anything occurs, on the basis of which it appears that the disadvantages of participation may be significantly greater than was foreseen in the research proposal. The study will be suspended pending

further review by the accredited METC, except in so far as suspension would jeopardise the subjects' health. The investigator will take care that all subjects are kept informed.

7.2 AEs, SAEs and SUSARs

7.2.1 Adverse events (AEs)

Adverse events are defined as any undesirable experience occurring to a subject during the study, whether or not considered related to IUI in natural cycle or IUI with letrozole. All adverse events reported spontaneously by the subject or observed by the investigator or his staff will be recorded.

Expected events will be reported by line listing once a year:

- Allergic reaction to medication
- Pregnancy related complications

7.2.2 Serious adverse events (SAEs)

A serious adverse event is any untoward medical occurrence or effect that at any dose:

- results in death;
- is life threatening (at the time of the event);
- requires hospitalisation or prolongation of existing inpatients' hospitalisation;
- results in persistent or significant disability or incapacity;
- is a congenital anomaly or birth defect;
- -any other important medical event that may not result in death, be life threatening, or require hospitalization, may be considered a serious adverse experience when based upon appropriate medical judgement, the event may jeopardize the subject or may require an intervention to prevent one of the outcomes listed above.

The sponsor will report within 15 days after the sponsor has first knowledge of the serious adverse reactions.

SAEs that result in death or are life threatening should be reported expedited. The expedited reporting will occur not later than 7 days after the responsible investigator has first knowledge of the adverse reaction. This is for a preliminary report with another 8 days for completion of the report.

7.3 Follow-up of adverse events

All AEs will be followed until they have abated, or until a stable situation has been reached. Depending on the event, follow up may require additional tests or medical procedures as indicated, and/or referral to the general physician or a medical specialist. SAEs need to be reported till end of study within the Netherlands, as defined in the protocol.

8. STATISTICAL ANALYSIS

Step 1: Summarizing trial data.

Baseline data and outcome data will be separately summarized. For continuous variables, we will examine the distribution of the observations, and if normally distributed then we will summarize them as means with standard deviations (SDs). If they are not normally distributed, then medians and inter-quartile ranges (IRQs) will be reported. For dichotomous data, we will provide proportions (or percentages). In addition to the baseline and outcome data, we will also summarize the recruitment numbers, those lost to follow-up, protocol violations and other relevant data.

Step 2: Inter-group comparisons.

The analysis of all outcomes will be done on an intention to treat basis.

The effectiveness of IUI with letrozole versus IUI in natural cycle will be expressed as a rate ratio for live birth with corresponding 95% confidence intervals. A formal test of the difference in rate will be performed using chi-square test statistics. The effectiveness over time will be evaluated in life tables and differences in live birth over time will be evaluated using the log-rank test. Further dichotomous outcomes will be analyzed using either Fishers Exact Test or chi-square as appropriate. For continuous outcomes we will use t-test if the observations in each trial arm are normally distributed, and if non-normally distributed, then Mann-Whitney-U test will be employed. Although p-values will be reported, the focus will be on providing 95% confidence intervals around point estimates as these are more useful in interpreting the findings of the trial.

Step 3: Adjustments and sensitivity analyses.

If randomization fails to achieve balanced groups, then we will perform secondary analyses in which we will adjust for unbalanced prognostic factors using procedures such as logistic regression. If the primary unadjusted analysis and secondary adjusted analysis are discordant, we will give greater weighting to the primary analysis in the interpretation of trial findings. For issues such losses to follow-up, missing data, and protocol violations, we will attempt sensitivity ("worst-case scenario") analyses to explore the effect of these factors on the trial findings. As a secondary analysis, we will adjust for missing data using imputation techniques to explore the effects of such imputations on the trial findings. The effect of baseline characteristics on the primary outcome will be explored using logistic regression analysis. In sub analyses the association between follicular growth and live birth will be evaluated.

Details of the analysis will be described in a separate statistical analysis plan, that will be developed during the study, and finalized before data lock.

Interim Analysis

Interim analysis will be done after completion data recruitment of the first 50 participants. An independent Data Safety Monitoring Committee (DSMC) will be invited. The DSMC will be asked to assess the endpoint ongoing pregnancy, as data on live birth will not be available. Also, the DSMC will be provided insight in the SAE's that have occurred. The continuation of the study will depend on the advice of DSMC. A formal stopping rule will be formulated in the separate statistical analysis plan.

Economic evaluation

An economic analysis will be performed alongside the clinical trial. The economic analysis will be performed from a healthcare perspective. Depending on the outcome of live birth rates in both groups, the economic analysis will be a cost-minimization of cost-effectiveness analysis.

Cost-effectiveness of each strategy will be presented as cost per live birth and costs

pre clinical pregnancy. Robustness of the results for various assumptions and parameter estimates will be explored in sensitivity analysis outcomes and will be expressed in ICER graphs and cost-effectiveness acceptability curves. A decision model will be used to evaluate the optimal strategy.

A distinction will be made between direct costs (costs like medical interventions and other healthcare costs like medical appliances) and indirect costs (costs of productivity loss or time loss costs). Costs will be measured in a subsample of participants.

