2. OBJECTIVES

Primary Objective:

To test the hypothesis that that in couples with unexplained or mild male factor infertility scheduled for an IUI program ovarian stimulation with letrozole increases the live birth rates over IUI in the natural cycle

We aim to answer the following questions:

What are after 3 cycles of IUI with letrozole and IUI in natural cycle;

- live birth rates
- multiple pregnancy rates
- financial costs

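### The normality rule sends costs to medians and a Mann-Whitney test, which do not estimate the mean cost difference that the planned economic analysis needs

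*Combined protocol and SAP*

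**What the plan says.** Section 8, Step 1 describes continuous data by mean and SD when normal. Otherwise: "If they are not normally distributed, then medians and inter-quartile ranges (IRQs) will be reported". Step 2 carries the same split into testing. Its first branch reads: "For continuous outcomes we will use t-test if the observations in each trial arm are normally distributed". The second branch, for skewed data, reads: "if non-normally distributed, then Mann-Whitney-U test will be employed".

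Section 6.1.2 lists "Direct and indirect costs" as the ninth secondary endpoint, and section 2 makes "financial costs" one of its three questions. Nothing in Steps 1 to 3 treats costs separately.

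The Economic evaluation part of section 8 says that, depending on the live birth rates, "the economic analysis will be a cost-minimization of cost-effectiveness analysis". It adds: "Cost-effectiveness of each strategy will be presented as cost per live birth and costs" per clinical pregnancy, with sensitivity results "expressed in ICER graphs and cost-effectiveness acceptability curves". It names no method for estimating or comparing mean cost. It also says that costs will be measured in a subsample, without giving its size. Section 8 leaves analysis details to a separate SAP, to be finalized before data lock.

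**The concern.** Most other endpoints in section 6.1.2 are counts of cycles or yes/no outcomes, and time to conception has life tables and the log-rank test. Cost is therefore the main outcome that the continuous-data rule governs.

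Cost per woman is unlikely to look normal. Most women use all three cycles, some stop early on conceiving, and a few may have very expensive care. The check would then select the median and the rank test. An ICER, a cost per live birth and a cost-minimization analysis all need the arithmetic mean cost per arm, because mean times number of women gives the total spent. A median does not have that property, and Mann-Whitney addresses whether a woman in one arm tends to cost more than a woman in the other. When the two cost distributions differ in shape, these quantities can differ in size or in sign. The trial would then give two answers to its cost question, with no rule on which one governs.

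**Working it through.** **Figures available.** The documents give no cost mean, SD or cost-subsample size, so there is no stated cost figure to reproduce. From section 4.4: 18% and 26% over three cycles, and 483 per arm. The 483 reproduces as 420 × 1.15 = 483 (two-sided 0.05, power 0.80). Since costs come from a subsample, 483 is only an upper bound here. Every cost input below is an assumption.

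**1. Would the rule select ranks?** Simulated costs were built from cycles used at the 18% and 26% rates, cycle costs of 100 to 115 units, and 1 to 5% of women with an extra cost averaging 1,500 to 2,000. A Shapiro test flagged non-normality in about 96 to 97% of trials at 50 per arm and in all trials at 200 or more. Without a high-cost tail and with moderate spread, a small subsample would be flagged less reliably.

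**2. Can median and mean differ in sign?** For a lognormal cost, mean = median × exp(s²/2), where s is the log-SD. Differences are letrozole minus natural.

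| Medians (letrozole, natural) | s (letrozole, natural) | Median difference | Means | Mean difference |
|---|---|---|---|---|
| 950, 1000 | 0.9, 0.6 | −50 | 1424, 1197 | +227 |
| 1100, 1000 | 0.5, 0.8 | +100 | 1246, 1377 | −131 |
| 950, 1000 | 0.6, 0.6 | −50 | 1137, 1197 | −60 |

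The sign reverses in the first two rows, where the shapes differ. It agrees in the third, where the shapes are the same.

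**3. Illustration from the plan's own rates.** Take a constant chance of conception per cycle.
- Per-cycle chance: 1 − 0.82^(1/3) = 0.0640 and 1 − 0.74^(1/3) = 0.0955.
- Mean cycles, 1 + (1−h) + (1−h)²: 2.812 natural, 2.723 letrozole.
- Assume that a letrozole cycle costs 2% more and that pregnancy costs are excluded: 1.02 × 2.723 = 2.777 against 2.812, so mean cost is 1.2% lower with letrozole. The break-even premium is 2.812/2.723 − 1 = 3.3%.

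The rank test can go the other way because most pairs of women use the same number of cycles. The probabilities of 1, 2 and 3 cycles are 0.064, 0.060, 0.876 (natural) and 0.0955, 0.086, 0.818 (letrozole). Hence P(letrozole uses more) = 0.107 and P(equal) = 0.728. With no spread between women, every equal pair counts as letrozole costlier: 0.107 + 0.728 = 0.835. If spread swamps the 2% premium, equal pairs split about evenly: 0.107 + 0.364 = 0.471, which agrees with the mean. The result therefore depends on the CV.

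Share of simulated trials in which Mann-Whitney significantly favours letrozole costlier, although its mean is lower, at 483 per arm:

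| Between-woman CV | Share |
|---|---|
| 2% | 100% |
| 5% | about 80% |
| 10% | 8 to 12% |
| 20 to 40% | 2% or less |

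At CV 5% the share falls to about 20 to 30% at 100 per arm and to 11 to 14% at 50 per arm.

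**4. Pregnancy costs.** If each pregnancy adds c cycle-costs, the means are 2.777 + 0.26c and 2.812 + 0.18c. They are equal at c = (2.812 − 2.777)/0.08 = 0.44. Above that, letrozole's mean is higher and the contradiction in step 3 disappears.

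**5. A missed difference.** Assume a lognormal base cost (median 3,000, s = 0.4) plus 30,000 in 3% of women in one arm and 0.5% in the other. The mean difference is 30,000 × 0.025 = 750, while the medians differ by about 38. Detection rates:

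| Per arm | Mann-Whitney | Comparison of means |
|---|---|---|
| 483 | about 10% | about 83% |
| 100 | 6% | 18 to 19% |
| 50 | 5% | 6% |

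**The case against.** The strongest reply is that costs have their own section. An ICER, an acceptability curve or a cost per live birth is not built from medians or rank statistics, so the economic section can be read as governing costs and implying means. Step 2 never mentions costs. This stands for the ICER itself: a reader should not infer that the ICER would be calculated from medians. It does not settle endpoint 9. The general rule covers it, the economic section neither exempts it nor names another comparison, and two conflicting cost results could be reported.

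A reader might also infer that the trial is likely to call letrozole costlier when it is cheaper, or to miss a large cost difference. The documents do not support that. The reversal in step 3 needs very small CVs, and the plan includes productivity and time-loss costs, which make CVs of 2 to 5% hard to believe. It also needs pregnancy costs to be excluded or small. The contrast of about 10% with 83% needs cost data on 483 women per arm, whereas the plan takes a subsample; at 50 per arm there is no contrast.

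Nor can one say that no interval would be reported. Step 2 puts the emphasis on 95% confidence intervals, and a Hodges-Lehmann interval can accompany Mann-Whitney; only its name is missing.

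Finally, details are deferred to a separate SAP. That is where the fix can go, but the rule here is already stated, and the later plan would inherit it unless it makes the exception.

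**Conclusion.** The point holds as a mismatch between a stated rule and the quantity that the plan's own economic analysis needs. Followed as written, the rule would almost always give medians and a rank test for costs, while cost-minimization, cost per live birth, the ICER and the acceptability curves need the arithmetic mean difference. That mismatch does not depend on sample size.

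Its practical size cannot be fixed from the documents. A disagreement in direction is possible and requires cost distributions of different shape in the two arms. With assumed inputs it ranges from near certain (CV 2%, 483 per arm) to 2% or less (CV 20 to 40%). Costs are a secondary endpoint measured in a subsample, and the live-birth comparison is untouched. This should be corrected before the SAP is finalized, but it does not threaten the trial's main conclusion.

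**What to change.** Add to Step 2, and carry into the separate SAP, wording such as:

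> Costs are exempt from the normality rule. They will be summarised as arithmetic means per woman in the cost subsample, by randomised arm, and compared as a mean difference with a non-parametric bootstrap 95% CI, whatever the distribution. Costs and effects will be bootstrapped jointly for the ICER and acceptability curves. Medians and IQRs are descriptive only.

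The cost is a few sentences and a short bootstrap program; no extra data are needed. The downside is that the interval may be wide if a few women have very high costs, especially in a small subsample. That width would reflect real uncertainty about mean cost.
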